3.5.3 Modified Rankin Scale

The mRS ranges from 0 to 6, ranging from perfect health without symptoms to death as follows:

- 0 - No symptoms
- 1 - No significant disability. Able to carry out all usual activities, despite some symptoms
- 2 - Slight disability. Able to look after own affairs without assistance, but unable to carry out all previous activities

- 3 - Moderate disability. Requires some help, but able to walk unassisted
- 4 - Moderately severe disability. Unable to attend to own bodily needs without assistance, and unable to walk unassisted
- 5 - Severe disability. Requires constant nursing care and attention, bedridden, incontinent
- 6 – Dead

Categories 5 and 6 will be combined for analysis purposes.

Treatment effect based on mRS score during RCP will be evaluated by Wilcoxon-Mann-Whitney Odds (WMWodds) approach (Appendix 5). Only the last post-baseline mRS score during RCP for each subject will be used for this analysis. Other post-baseline scores will be presented descriptively using count and percentage in each mRS category (with 5 and 6 combined into a single category) and shift from baseline.

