4.8.7 Additional Analyses

An exploratory analysis of time to AC-determined NMO/NMOSD attack or rescue therapy without an AC-determined NMO/NMOSD attack during the RCP will be conducted by considering rescue therapy as events of interest as well. Subjects who never experience any AC-determined NMO/NMOSD attack nor receive rescue therapy will be censored for this analysis.

The agreement between site-determined NMO/NMOSD attack and AC- determined NMO/NMOSD attacks will be assessed by Kappa statistic.

An inter- and intra-rater reliability assessment will be performed based on a random selection of all events contributing to the primary analysis.

A shift analysis of the scores from the mRS will be performed.

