3.3.2.4 Neurological Examination

Presence of significantly abnormal neurological finding will be summarized by Number (%) of subjects in each category for ITT population.

Table 3.3.2.4-1 Baseline Characteristics

 Type of original diagnosis [NMO, NMOSD] - n (%) Disease duration (years) defined as the years between date of diagnosis and date of 1st administration of IP, calculated as (date of 1st IP administration - date of diagnosis + 1)/365.25 - descriptive statistics Disease duration category (< 5 years, ≥ 5 years) - n (%) Type of 1st relapse [ON, Myelitis, Brain/Brainstem] - n (%) Most recent NMO relapse type prior to 1st IP administration [ON, Myelitis, Brain/Brainstem] - n (%) Number of prior relapse category [1, 2, 3, 4 etc.] - n (%) Annualized relapse rate prior to 1st IP administration, calculated as total number of relapses (irrespective of type) normalized by total person-years; the person-year for each subject will be defined by the time (years) since 1st NMO/NMOSD relapse as defined below - descriptive statistics Time (years) since 1st NMO/NMOSD relapse defined as the years between date of 1st relapse and date of 1st administration of IP, calculated as (date of 1st IP administration - date of 1st relapse + 1)/365.25 - descriptive statistics Annualized relapse rate prior to 1st IP administration based on relapse type reported (ON, Myelitis, Brain/Brainstem) - descriptive statistics Tested for AQP4-IgG prior to randomization (yes/no) - n (%) AQP4-IgG seropositive prior to randomization - n (%) Age (years) at diagnosis- descriptive statistics Age (years) at 1st relapse- descriptive statistics Smoking status Never, Ever - n (%) If ever smoked, current and former but not current - n (%) If former but not current smoker, number of years since cessation - descriptive statistics If current smoker, smoking duration (years) - descriptive statistics If ever smoked, Average number of cigars/day - descriptive statistics Average number of pipes/day- descriptive statistics 	
 EDSS - n(%), descriptive statistics EDSS category [0, 1-5, > 5] - n (%) Functional Systems Scores - n(%), descriptive statistics Monocular visual acuity score [Low and high contrast], left (OS) and right (OD) eye - descriptive statistics Binocular visual acuity score [Low and high contrast] - descriptive statistics Counting Fingers (CF), Hand Movement (HM), Light Perception (LP), No Light Perception/Total Blindness (NLP) - n (%) RAPD (OS), RAPD (OD), No RAPD - n (%) Pupil response score (OD and OS) (1+, 2+, 3+, 4+ and 5+) - n (%) AQP4-IgG titer level based on flow cytometry assay (FACS) Total number of Gd-enhancing lesions, by locations (Brain, Brainstem, Spinal cord, Optic nerve (left and right eye combined)) and overall - descriptive statistics Co-existing autoimmune disease category [Active, Asymptomatic, Remission] (Rheumatoid arthritis, Autoimmune thyroiditis, Celiac disease, Systemic lupus, Sjögren’s syndrome, Insulin dependent diabetes mellitus (IDDM), Myasthenia gravis, Pernicious anaemia, Other) - n(%) Modified Rankin scale (mRS) score (0, 1, 2, 3, 4, 5/6) - n (%) Worst Pain level during past 24 hours (eyes, upper back, lower back, arms, and legs) - descriptive statistics SF-36 (4-week recall) domain scores - descriptive statistics Columbia-Suicide Severity Rating Scale (C-SSRS) categories (see Section 3.7.4.1 for definition) for both lifetime and baseline (past 6 months) - n (%) Chest X-ray [normal, abnormal] - n (%) Vital signs (see section 3.7.4.2) - descriptive statistics, n (%) Electrocardiogram (ECG) (see section 3.7.4.3) - descriptive statistics, n (%) TB test results [Positive, Negative, Indeterminate] - n (%)

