3.5.1.1 Analysis of Pain Scale

Actual value and change from baseline of the pain scores for each body location (eyes, legs, arms, upper back, and lower back) will be summarized descriptively over all visits during RCP and OLP. The pain score averaged over all locations will be summarized.

Treatment effect for pain based on change from baseline at the last visit of the RCP will be tested using analysis of covariance models using treatment and baseline pain NRS scores as explanatory variables. Last non-missing value during RCP will be used for this analysis.

Another supportive analysis will be implemented using mixed effects model repeated measures (MMRM) approach. In this model, change from baseline will be dependent variable; baseline pain score, treatment and time will be used as independent variables. An

interaction term of treatment and time will also be included. The Kenward-Roger approximation will be used to estimate denominator degrees of freedom and adjust standard errors. The treatment difference will be obtained with LSMEAN statement from SAS PROC MIXED for the treatment difference at a specified visit. An unstructured within subject error covariance matrix will be used for this model. Subjects' last value during RCP will be aligned with next closest scheduled visit in order to use all information available.

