3.5.2.1 Analysis of SF-36 Health Survey

Actual value, change and percent change from baseline of SF-36 scores will be summarized descriptively over all visits during RCP and OLP.

Treatment effect based on SF-36 PCS will be tested using an ANCOVA model using treatment and baseline SF-36 PCS score as explanatory variables. Similar analysis will be done for SF-36 MCS and the 8 remaining domains.

Another supportive analysis for PCS and MCS change scores during RCP will be implemented using mixed effects model repeated measures (MMRM) approach as described in section 3.5.1.1.

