Appendix 5 WMWodds approach for mRS score analysis

Treatment effect based on mRS score during RCP will be evaluated by the WMWodds approach ([Divine et al.](#), [Churilov et al.](#)). This procedure estimates the odds that for two subjects chosen at random with one from each treatment group, the subject who received the investigational product will have a better outcome than the subject receiving standard treatment. Consider all possible pairs of observations where the first observation is taken from the MEDI-551 group (Y_T) and the second observation is taken from the placebo group (Y_C). If group Y_T included n observations and group Y_C included m observations, the two-group comparison would lead to the total of $n \times m$ pairs of observations. In each pair, the observation from the MEDI-551 arm will either be worse than the placebo observation, the same as the placebo observation, or better than the placebo observation. The probabilities that in a randomly chosen pair of MEDI-551 and placebo subjects, the MEDI-551 subject has worse outcome ($\text{Prob}(Y_T > Y_C)$), the same outcome ($\text{Prob}(Y_T = Y_C)$), or better outcome ($\text{Prob}(Y_T < Y_C)$), can then be estimated as the ratio of the number of pairs satisfying each of these individual conditions to the total number of $n \times m$ pairs. Given the possibility of tied observations between two treatment groups, the null hypothesis can be stated that the probability a subject under MEDI-551 treatment is worse than placebo is the same as the probability that a MEDI-551 treated subject is better than placebo accounting for ties, in other words, the probabilities $\text{Prob}(Y_T > Y_C) + 0.5\text{Prob}(Y_T = Y_C)$ and $\text{Prob}(Y_T < Y_C) + 0.5\text{Prob}(Y_T = Y_C)$ both being equal to 0.5. Thus, WMWodds test statistic is defined as follows:

$$\text{WMWodds} = \frac{\text{Prob}(Y_T < Y_C) + 0.5\text{Prob}(Y_T = Y_C)}{\text{Prob}(Y_T > Y_C) + 0.5\text{Prob}(Y_T = Y_C)}$$

Table 7-11 provides conceptual framework to identify number of pairs where mRS scores (5 and 6 combined together) in MEDI-551 group is same, better or worse than corresponding Placebo group scores. WMWodds is then defined by

$$= \frac{\text{Number of MEDI - 551 better pairs} + 0.5 \times \text{Number of tied pairs}}{\text{Number of MEDI - 551 worse pairs} + 0.5 \times \text{Number of tied pairs}}$$

The WMWodds and 95% CI will be calculated based on area under the curve (concordance index) from logistic regression.

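### The mRS treatment comparison does not use the Day 1 mRS, which costs precision in a supportive analysis

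*SAP*

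**What the plan says.** Protocol Table 6 schedules the mRS on Day 1 and at later visits of the Randomized-controlled Period (RCP), and SAP Table 3.3.2.4-1 tabulates it as a baseline characteristic. For the analysis, Protocol 4.8.7 says only: "A shift analysis of the scores from the mRS will be performed". It names no model, test or covariate.

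SAP 3.5.3 makes WMWodds the method for the treatment effect and restricts the data: "Only the last post-baseline mRS score during RCP for each subject will be used for this analysis". It continues: "Other post-baseline scores will be presented descriptively using count and percentage in each mRS category", together with shift from baseline. Appendix 5 defines the odds from pairs of final scores, one from each arm, and gives the computation: "The WMWodds and 95% CI will be calculated based on area under the curve (concordance index) from logistic regression". No covariate is named there.

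Other scored measures are handled differently. Pain is "tested using analysis of covariance models using treatment and baseline pain NRS scores as explanatory variables" (SAP 3.5.1.1). For quality of life, SAP 3.5.2.1 says: "Treatment effect based on SF-36 PCS will be tested using an ANCOVA model using treatment and baseline SF-36 PCS score as explanatory variables". EDSS worsening and low-contrast acuity (SAP 3.4.2.3) and AQP4-IgG titer (SAP 3.6.1.2) are also modelled with their baseline values.

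Randomisation is stratified by serostatus and region only (SAP 2.3).

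**The concern.** A disability score taken within 28 weeks of entry is likely to be related to the score at entry. If so, part of the spread in final mRS is between-subject variation that was already present on Day 1. An unadjusted comparison keeps that variation as noise. Baseline adjustment removes it and also corrects for whatever imbalance chance has produced. No stratification factor is a disability measure, so the design does nothing specific to balance baseline mRS, and the placebo arm is the smaller one, at 63 planned subjects.

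At stake are the precision of the WMWodds and how it reads if the arms happen to differ at entry. The data needed for adjustment are already collected.

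**Working it through.** **1. The plan's own figure.** The documents give no power, effect size or correlation for the mRS. Their one sizing figure is the 67 attacks for the primary endpoint. The SAP Appendix 1 formula gives [(1.960 + 1.2816)/ln 0.4]² × (3+1)²/3 = 66.75, rounded up to 67, which agrees. The planned 252 subjects at 3:1 give 252 × 3/4 = 189 on MEDI-551 and 63 on placebo.

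**2. Where the SAP uses baseline in a treatment test.**

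| Measure | SAP section | Own baseline in the test |
|---|---|---|
| EDSS worsening | 3.4.2.3 | yes |
| Low-contrast acuity | 3.4.2.3 | yes |
| Pain NRS | 3.5.1.1 | yes |
| SF-36 | 3.5.2.1 | yes |
| AQP4-IgG titer | 3.6.1.2 | yes |
| Active MRI lesions | 3.4.2.3 | no |
| mRS | 3.5.3, Appendix 5 | no |

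**3. Power at 189 versus 63.** Simulation with 2,000 trials per row and effect, two-sided 5%. The following are assumptions, not figures from the documents:
- mRS shares for 0, 1, 2, 3, 4 and 5/6 of 8, 27, 28, 20, 14 and 3%;
- a bivariate normal latent scale with baseline-to-final correlation ρ;
- a uniform latent shift of 0.3 SD (WMWodds about 1.37) or 0.4 SD (about 1.54).

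Three tests were compared: the planned unadjusted rank test; rank ANCOVA (rank of final mRS on rank of baseline mRS and treatment); and van Elteren (rank sums within each baseline category, weighted by 1/(stratum size + 1)).

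| ρ | 0.3 SD: unadjusted / rank ANCOVA / van Elteren | 0.4 SD: unadjusted / rank ANCOVA / van Elteren |
|---|---|---|
| 0.3 | 48.2 / 50.2 / 48.9% | 74.0 / 77.5 / 77.2% |
| 0.5 | 49.8 / 57.6 / 57.3% | 71.6 / 81.4 / 80.2% |
| 0.7 | 48.6 / 71.5 / 70.8% | 73.8 / 91.5 / 91.9% |
| 0.8 | 48.1 / 83.0 / 83.4% | 73.4 / 97.8 / 97.7% |
| 0.9 | 50.3 / 95.5 / 95.6% | 73.9 / 99.7 / 99.6% |

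Rank ANCOVA minus unadjusted, at 0.3 and 0.4 SD: 2.0 and 3.5 points at ρ = 0.3; 7.8 and 9.8 at 0.5; 22.9 and 17.7 at 0.7; 34.9 and 24.4 at 0.8. A single power figure has a simulation standard error of at most √(0.5 × 0.5/2000) = 1.1 points.

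**4. Hand check of one cell (ρ = 0.7, 0.4 SD).** Unadjusted power of 73.8% means an expected Z of 1.960 + 0.637 = 2.597. The simulated rank correlation between baseline and final score is 0.64. Adjustment divides the standard error by about √(1 − 0.64²) = 0.768 relative to its old value of 1, so Z becomes 2.597/0.768 = 3.38. Power is then Φ(3.38 − 1.96) = Φ(1.42) = 92%, against 91.5% simulated.

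**5. Validity and chance imbalance, with no treatment effect.** The unadjusted test rejects in 4.7 to 5.2% of all trials across the five correlations, so it holds its level. In trials where the baseline rank test has |Z| > 1.5, which chance produces 2 × (1 − Φ(1.5)) = 13% of the time, its rejection rate is:

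| ρ | Unadjusted | Rank ANCOVA |
|---|---|---|
| 0.3 | 8.4% | 4.6% |
| 0.5 | 10.4% | 3.0% |
| 0.7 | 15.8% | 5.0% |
| 0.8 | 23.1% | 4.0% |

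Each row rests on about 0.134 × 2,000 = 267 trials. When MEDI-551 is worse at baseline with Z between 1 and 2, the unadjusted WMWodds averages 0.93, 0.90, 0.88 and 0.83 for these four correlations, where the true value is 1.00.

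**The case against.** The strongest reply is that the comparison is randomised. Baseline differences are zero in expectation, and the variance of the unadjusted test already allows for chance imbalance. That stands. A reader might infer that the test mainly measures how disabled the arms were at entry. The documents do not support this. On the latent scale, baseline accounts for ρ² of the random variance of the arm difference, which is 9% at ρ = 0.3 and 25% at 0.5, and passes half only above √0.5 = 0.71. No value of ρ is given.

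The correlation could also be lower than intuition suggests. The last RCP score need not be a Day 197 score: subjects with an adjudicated attack may leave for the open-label period, and Protocol Table 8 schedules the mRS at the Assessment Visit. Against that, 67 attacks in 252 subjects leaves 1 − 67/252 = 73% without one. Neither fact settles the value.

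A reader might also infer that the SAP contradicts the protocol's shift analysis, or discards baseline mRS altogether. Neither holds. The protocol sentence specifies no model, and the SAP provides a descriptive shift from baseline and a baseline table. The gap is confined to the inferential comparison.

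Finally, WMWodds is a reasonable choice for an ordinal scale and assumes little, and the SAP is not uniform about baseline, as the MRI lesion model shows. Both points stand. They argue against replacing the method with a proportional-odds model, but not against stratifying it.

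**Conclusion.** The point holds as a modest improvement. The only inferential mRS analysis leaves out a baseline value that the trial collects, whereas five other treatment tests in the SAP use theirs. The planned test is not biased and keeps its 5% level. It loses precision, and the realised estimate carries any chance imbalance.

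The size of the loss turns on the baseline-to-final correlation: close to nothing at 0.3, material at 0.5, large at 0.7 and above. The correlation, effect size, category shares and uniform latent shift are all assumptions. The 252 subjects are the planned maximum. Enrolment may stop earlier, which would lower power for every test.

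The consequence is limited. The mRS is absent from the endpoint lists in Protocol 2.2.1 to 2.2.3, appears under additional analyses in Protocol 4.8.7, and is not among the ten hypotheses of SAP Appendix 3. A reader should not infer that the primary or key secondary conclusions are affected.

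**What to change.** Before unmasking, amend SAP 3.5.3 and Appendix 5 as follows.
- Make the mRS comparison a WMWodds with a van Elteren test, stratified by baseline mRS category. Rank ANCOVA on baseline mRS is an acceptable alternative.
- State in advance how sparse baseline categories are pooled. At the assumed 3% share, category 5/6 would hold about 0.03 × 63 = 2 placebo subjects.
- Keep the unadjusted WMWodds as supportive. The stratified odds compares subjects with the same entry score, so the two estimates are not interchangeable and should be labelled.
- Use proportional-odds regression, if at all, only as a further sensitivity analysis, because it changes the estimand and adds an assumption.
- Say that the shift-from-baseline table, extended to the last RCP score, is what meets Protocol 4.8.7.

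The cost is SAP wording and minor programming. No new data are needed. If the adjustment is chosen only after unmasking, it should be reported as post hoc.

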3.5.4 Other Efficacy Analyses

Table 3.5.4-1 provides an overview of additional efficacy analyses to be performed.

Table 3.5.4-1 Additional Efficacy Analyses

Type of analysis	Analysis Method	Analysis population
Cox proportional hazards model of investigator-determined NMO/NMOSD attack	Similar analysis as primary endpoint but based on investigator-determined NMO/NMOSD attack.	ITT
Time to either AC-determined NMO/NMOSD attacks or rescue therapy	An exploratory analysis of time to adjudicated AC-determined NMO/NMOSD attacks or rescue therapy (where an attack has not been determined by AC) during the RCP will be conducted by considering administration of rescue therapy as an event of interest. Subjects who never experience an NMO/NMOSD attack (determined by AC) nor received any rescue therapy will be censored for this analysis. In the instance where a subject never experiences an AC-determined NMO/NMOSD attack, the time to rescue therapy will be used for this analysis.	ITT
Type of NMO/NMOSD attacks	Number (%) of subjects with different types of NMO/NMOSD attacks (ON, Myelitis, Brain and Brainstem) (subjects will be included in multiple categories if applicable): 
 • Based on AC-determined attacks • Based on investigator-determined attacks 	ITT
Summary of individual criteria of NMO/NMOSD attack	Number (%) of subjects meeting each of the protocol-defined criteria for NMO/NMOSD attack will be summarized descriptively (subjects will be included in multiple categories if applicable): 
 • Based on AC-determined attacks • Based on investigator-determined attacks 	ITT
Criteria based severity of attack	Number (%) of subjects meeting each of the protocol-defined criteria of an AC-determined NMO/NMOSD attack will be summarized broken down by the severity [mild, moderate, severe] defined in Table 3.4.1.4-1	ITT
Attack type based severity	Number (%) of subjects meeting an AC-determined NMO/NMOSD attack will be summarized broken down by the severity [minor, major] defined in Appendix 4	ITT

Table 3.5.4-1 Additional Efficacy Analyses

Type of analysis	Analysis Method	Analysis population
Attack recovery	Number (%) of subjects meeting an AC-determined NMO/NMOSD attack will be summarized broken down by the recovery status [minor, major] defined in Appendix 4	ITT
Summary of symptoms of AC-determined NMO/NMOSD attacks	Number (%) of subjects broken down by different type of NMO symptoms who experienced an AC-determined attack. Subjects will be included in multiple categories if applicable. A separate summary of the percentage based on number of AC-determined attack will also be provided.	ITT
Concordance between NMO relatedness assessment between AC and investigator	Number (%) of cases by relatedness to NMO [related, not related] for each reported symptom where AC agrees or disagrees with investigators' assessment. The denominator will be the number of cases reported rather than subjects.	ITT
EDSS	Descriptive summary of change from baseline by visit	ITT and OL
EDSS category	Number (%) of subjects for EDSS category [0, 1-5, > 5] by visit	ITT and OL
EDSS worsening	Number (%) of subjects meeting EDSS worsening by visit	ITT and OL
Functional Systems Scores	Descriptive summary of change from baseline by visit	ITT and OL
MRI	
Descriptive summary MRI lesion by location (Optic nerve, Spinal cord, Brain and Brainstem) and overall during RCP and OLP
 
 • cumulative new Gd-enhancing lesions • cumulative new/enlarging T2 lesions • cumulative active lesions (sum of cumulative new Gd lesions and new/enlarging T2 lesions that are not associated with a Gd lesion) 	ITT and OL
Visual acuity score	
Descriptive summary of change from baseline by visit for the following (low and high contrast):
 
 • monocular score, left (OS) and right (OD) • binocular score 	ITT and OL
Other visual acuity parameters	
Number (%) of subjects by visit for the following:
 
 • Counting Fingers (CF), Hand Movement (HM), Light Perception (LP), No Light Perception/Total Blindness (NLP) • RAPD (OS), RAPD (OD), No RAPD • Pupil response score (OD and OS) (1+, 2+, 3+, 4+ and 5+) 	ITT and OL

Table 3.5.4-1 Additional Efficacy Analyses

Type of analysis	Analysis Method	Analysis population
Other analyses related to in-patient Hospitalizations (secondary endpoint)	Number (%) of subjects: 
 • With at least one in-patient hospitalization • With at least one in-patient hospitalization or AC-determined attack • With number of in-patient hospitalizations (1, 2, >2) Descriptive summary: 
 • Mean number of in-patient hospitalization per subject • Mean days with in-patient hospitalization per subject 	ITT and OL

3.6 Pharmacodynamic Endpoint(s) and Analyses

3.6.1.1 Pharmacodynamic Endpoint(s)

The following PD endpoints will be analyzed:

- AQP4-IgG titer level and change from baseline
- B-cell absolute counts and percentage based on baseline
- Change from baseline in plasma gene signature

3.6.1.2 Analysis of Pharmacodynamic Endpoints

AQP4-IgG titer levels and corresponding change from baseline will be summarized by visit. Change from baseline will be analyzed based on the ANCOVA model with baseline value and treatment as explanatory variables.

Change from baseline by visit in plasma gene signature will be summarized descriptively for all subjects and by serostatus at screening.

B-cell (CD-19 and CD-20) absolute counts and corresponding percentage based on baseline will be summarized descriptively by visit.

